8.5.1 Study Stopping Rules

Enrollment will be paused if any of the following events are identified and the DSMB determines that there is probable cause that the IP or enema procedure contributed to the event:

1. There is probable cause that IP or enema procedure (e.g., due to transfer from an RBX2660 donor) contributed to a pathogenic intestinal infection in the stool of any subject, or
2. Any series of events of major significance such as death or other serious outcome for which a causal connection with the IP is plausible represents an excess of the important adverse event(s) in one of the study arms.

8.6 Multi-center Studies and Pooling of Centers

The study will be conducted at up to 80 clinical study sites in the US and Canada.

This is a multicenter study and before data from all sites are pooled, the effect of site will be assessed for the primary efficacy endpoint. A sufficient number of subjects (≥ 7 meeting the PP definition) will be required within each investigative site to determine if there are any outlying sites. If an investigative site is unable to enroll a sufficient number of subjects, it may be necessary to combine smaller sites (where enrollment is too low to detect differences) to create “pseudo-sites”. Sites with < 7 subjects will be considered eligible for pooling. Eligible sites will be pooled sequentially with other sites in the same region until a sufficient number of subjects are reached (at least seven).

In this process, sites with < 7 subjects will be ordered numerically in ascending order, based on the investigative site number. Sites with < 7 subjects will then be sequentially pooled with other sites in the same region in ascending order by site number until the resulting pseudo-site has at least 7 subjects meeting the PP population definition, thus creating a new “pseudo-site”. The process will begin again with the next sequential small site until all small sites have been pooled with other sites in the same region into a pseudo-site. Pooling of the centers will be done prior to study unblinding.

The proportions and 95% confidence intervals for the primary efficacy endpoint data will be presented by pseudo-site to determine if any outlying sites exist.

8.7 Multiple Comparisons/Multiplicity

A hierarchical closed-testing procedure will be utilized for the primary and the secondary efficacy endpoint as noted in Section 7.6.1.1.

8.8 Examination of Subgroups

Subgroup analysis of age (< 65 years, ≥ 65 years), sex (Female, Male), race group (White, Non-white), ethnicity (Hispanic-Latino, not Hispanic-Latino), site geography (outside the US, Eastern

US*, Southern US*, Northern US*, Western US*) and number of previous episodes of CDI recurrence at baseline will be conducted on the primary efficacy analysis if a sufficient sample size exists for each subgroup. The primary efficacy analysis will also be conducted based on vancomycin use for the qualifying CDI episode \leq 14 days and $>$ 14 days using subjects who were stratified based on Vancomycin Alone. These analyses will include all analysis populations (mITT and PP) to understand any differences.

*States included in the identified US geographical regions are as follows:

- Eastern US: Connecticut, Delaware, District of Columbia, Maine, Maryland, Massachusetts, New Hampshire, New Jersey, New York, Ohio, Pennsylvania, Rhode Island, Vermont, Virginia, West Virginia
- Southern US: Alabama, Arkansas, Georgia, Florida, Kansas, Kentucky, Louisiana, Mississippi, North Carolina, Oklahoma, South Carolina, Tennessee, Texas
- Northern US: Illinois, Indiana, Iowa, Michigan, Minnesota, Missouri, Nebraska, North Dakota, South Dakota, Wisconsin
- Western US: Arizona, California, Colorado, Idaho, Montana, Nevada, New Mexico, Oregon, Utah, Washington, Wyoming

Other sub-groups may be considered if there are enough subjects in each group such as; qualifying CDI event treated as inpatient vs. outpatient, the severity of the qualifying event based on the ATLAS scores, treatment length or type of antibiotics taken at the time of the CDI qualifying event, and others yet undetermined.

Cochran-Mantel-Haenszel tests will be used to assess homogeneity of the odds ratios in the subgroups.

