4.4 Determination of Sample Size

To demonstrate a 69% success with one dose of the RBX2660 treatment group vs. 47% success in the Placebo control group, 240 subjects are required (power > 90%, nominal 2.5% type I error rate). Up to an additional 30 subjects will be enrolled to allow for a 10% loss-to-follow up rate, for a total of approximately 270 subjects. Considering the 2:1 randomization, this results in approximately 180 subjects in the RBX2660 arm and 90 subjects in the Placebo arm. Enrolled subjects who have signed consent and withdraw for any reason prior to administration of the first blinded enema will be replaced without counting toward the sample size cap. Replacement subjects will be randomized to ensure proper blinding.

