An analysis of time to CDI recurrence after completion of the assigned blinded treatment will be analyzed and presented by the Kaplan-Meier procedure and median duration presented by days (and weeks) using the ITT, mITT, and PP populations. The Kaplan-Meier estimate of the median time (days) and the associated 95% confidence interval will be presented for each treatment group. A graphic presentation of the Kaplan-Meier estimates will supplement the tabular presentation. Between group comparisons will be performed using the stratified log-rank test based on the stratification factor at randomization. The corresponding hazard ratio of the treatment effect along with the 95% confidence interval will be calculated using a Cox proportional hazard model with treatment and the stratification factor at randomization as explanatory variables.

Time to CDI recurrence is defined as the number of days from enema administration to first assessment indicating recurrence for those subjects who were deemed Treatment Failures with CDI recurrence. All subjects who are Indeterminate or discontinued for any reason prior to assessment of efficacy will be censored at the last assessment date at/prior to Week 8. For the analysis of Time to CDI recurrence within 8 weeks, all subjects considered as a treatment success will be censored at the date of their 8-week assessment. For the analysis of Time to CDI

recurrence through 6 months, all subjects considered to have achieved sustained clinical response will be censored at the date of their 6-month assessment.

Finally, the sensitivity of the primary efficacy endpoint will be assessed in a multivariate logistic regression adjusting for possible interactions of the following covariates with treatment group: age (< 65 years, \geq 65 years), sex (Female, Male), race group (White, Non-white), ethnicity (Hispanic-Latino, not Hispanic-Latino), site geography (outside the US, Eastern US*, Southern US*, Northern US*, Western US*), randomization strata (i.e., treatment received at the qualifying event) and number of previous episodes of CDI recurrence at baseline. Other baseline variables will be compared for balance using the appropriate statistical test. This analysis will be performed on all analysis populations where at least 20 subjects in each sub-group are available for analysis to fully understand the observed treatment effect.

*States included in the identified US geographical regions are as follows:

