8 STATISTICAL METHODS

8.1 General Methodology

All statistical tests will be two-sided with a significance level of $\alpha=0.05$, unless specified otherwise, and will be performed using SAS® Version 9.3 or higher. Confidence intervals (CI) will be constructed at the level of 95% unless specified otherwise. For continuous variables,

descriptive statistics (number of subjects [N], mean, standard deviation [SD], median, interquartile range [IQR], minimum, and maximum) will be generated. For discrete/categorical variables, the number and percentage of non-missing subjects will be generated. Descriptive statistics will be provided by treatment arm for all subjects. Standard operating procedures (SOPs) will be followed in the creation, validation and quality control of all data displays and analyses.

Subject listings of all data from the eCRFs as well as any derived variables will be presented.

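### SAP 8.8 assigns Cochran-Mantel-Haenszel tests to check that subgroup odds ratios are homogeneous, but that test asks whether a common odds ratio equals 1 and does not measure differences between subgroups

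*SAP*

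**What the plan says.** SAP 8.8 lists the subgroups for the primary efficacy endpoint: age, sex, race, ethnicity, site geography and number of previous CDI episodes. It then adds one prespecified split within the Vancomycin Alone stratum, 14 days or less against more than 14 days: "The primary efficacy analysis will also be conducted based on vancomycin use for the qualifying CDI episode". Further subgroups are optional: "Other sub-groups may be considered if there are enough subjects in each group such as", followed by examples that include inpatient or outpatient treatment, ATLAS severity, and length or type of antibiotic treatment. The section ends with the sentence at issue: "Cochran-Mantel-Haenszel tests will be used to assess homogeneity of the odds ratios in the subgroups".

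SAP 7.6.1.2 plans a separate sensitivity analysis, a "multivariate logistic regression adjusting for possible interactions of the following covariates with treatment group". Its covariates are all the factors in the main 8.8 list plus the randomisation strata. It carries a size condition: "This analysis will be performed on all analysis populations where at least 20 subjects in each sub-group are available for analysis". Section 8.8 does not refer to it.

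Neither document names Breslow-Day, Tarone, Zelen or any other test of equal odds ratios. SAP 8.7 limits multiplicity control to the main endpoints: "A hierarchical closed-testing procedure will be utilized for the primary and the secondary efficacy endpoint as noted in Section 7.6.1.1".

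**The concern.** The stated purpose and the named test do not match. Homogeneity means that the odds ratios are equal to each other, whatever their value. CMH tests conditional independence, meaning that a common odds ratio across strata equals 1. A drug that works equally well in every subgroup satisfies the first hypothesis and violates the second.

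If 8.8 is followed literally, the report would print a p-value labelled as a homogeneity test that is usually small in a trial where the drug works uniformly. A reader could then infer that the effect differs by age, sex or region when it does not. Conversely, where effects run in opposite directions in subgroups of similar size, the same p-value would usually look reassuring. What is at stake is the reading of the subgroup tables.

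**Working it through.** **Inputs.** Success rates are from SAP 4.4: "69% success with one dose of the RBX2660 treatment group vs. 47% success in the Placebo control group". The total of 240 is also from SAP 4.4; at 2:1 it gives 160 RBX2660 and 80 placebo. The test level is from SAP 8.1: "All statistical tests will be two-sided with a significance level of" 0.05. Subgroup sizes are not in the documents, so a range is used.

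**Step 1. Reproduce the plan's sample size.** The subgroup test has no figure of its own, so this step only confirms the rates and arm sizes. For 2:1 allocation, placebo n = [1.960·√(p̄q̄·1.5) + 1.282·√(p₀q₀ + p₁q₁/2)]² / (p₁ − p₀)².

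- p̄ = (0.47 + 2 × 0.69)/3 = 0.6167, so p̄q̄ = 0.2364 and the first term is 1.960 × 0.5955 = 1.167.
- The second term is 1.282 × √(0.2491 + 0.2139/2) = 0.765.
- n = (1.932)²/0.0484 = 77.1, rounded up to 78. The total is 3 × 78 = 234, within 3% of the stated 240.
- Power at 160/80 is 0.910, consistent with the stated power above 90%.

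**Step 2. Fixed-count example.** For each subgroup, a is the number of RBX2660 responders, E = n₁m/n and V = n₁n₀m(n − m)/[n²(n − 1)], where n₁ and n₀ are the arm sizes, n their sum and m the responders in both arms. Then CMH = (Σ(a − E))²/ΣV on 1 df, without continuity correction.

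*Equal effects:* 55/80 vs 19/40 in both subgroups (odds ratio 2.43 in each).
- E = 80 × 74/120 = 49.33 and V = 80 × 40 × 74 × 46/(120² × 119) = 6.357.
- CMH = (2 × 5.667)²/(2 × 6.357) = 10.10, p = 0.0015.
- Breslow-Day-Tarone p = 1.00.

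*Opposite effects:* the second subgroup becomes 38/80 vs 28/40 (odds ratios 2.43 and 0.39).
- In that subgroup E = 80 × 66/120 = 44, so a − E = −6, and V = 6.656.
- CMH = (5.667 − 6)²/(6.357 + 6.656) = 0.0085, p = 0.93.
- Breslow-Day-Tarone p = 0.0012.

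The p-value labelled homogeneity is small when the odds ratios are identical and large when they are opposite.

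**Step 3. Rejection rates over repeated trials.** 200,000 simulated trials per scenario, independent binomials, two subgroups, 160/80 in total, two-sided 0.05. Breslow-Day-Tarone compares each a with its expectation at the Mantel-Haenszel odds ratio.

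| Split of subjects | Same effect: CMH | Same effect: Breslow-Day-Tarone | Opposite effects: CMH | Opposite effects: Breslow-Day-Tarone |
|---|---|---|---|---|
| 50/50 | 91% | 5.2% | 4% | 91% |
| 60/40 | 91% | 5.2% | 9% | 90% |
| 70/30 | 91% | 5.2% | 25% | 86% |
| 80/20 | 91% | 5.3% | 51% | 76% |
| 90/10 | 91% | 5.6% | 75% | 52% |

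Same effect is 69% vs 47% in both subgroups. Opposite is 69% vs 47% in the larger and 47% vs 69% in the smaller. At 50/50 the Wald test of the logistic interaction rejects in 5.1% and 90.7%, close to Breslow-Day-Tarone.

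Other cases at 50/50, CMH against Breslow-Day-Tarone:
- No effect in either subgroup (47% vs 47%): 5.0% and 5.0%.
- Benefit in one subgroup only: 36.7% and 38.3%.
- 69% and 90% vs 47% (the 90% is an assumption): 99.9% and 61.6%.

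**Step 4. The vancomycin-duration split.** The documents give neither the Vancomycin Alone share nor the duration split. Assume a share of 40%, 60% or 80% of 240, with 30%, 50% or 70% in one duration group. Over the nine combinations:
- Equal effects: CMH is significant in 55–84% of trials, Breslow-Day-Tarone in 5.2–5.5%.
- Opposite effects: CMH 4–22%, Breslow-Day-Tarone 50–84%.

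**The case against.** **The purpose is clear, so a competent statistician would run the right test.** The sentence may be shorthand for a homogeneity test reported alongside CMH. That is possible and the documents cannot settle it. But the only test they name is CMH, and if another was meant, naming it costs nothing.

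**Heterogeneity is already examined elsewhere.** This largely stands. A reader might infer that the plan has no valid look at effect differences; that would be wrong. The 7.6.1.2 interaction model covers every factor in the main 8.8 list, and its randomisation-strata term partly overlaps the optional antibiotic-type subgroup, since the strata are antibiotic types. The model is conditional on 20 subjects per sub-group, and it omits vancomycin duration, inpatient/outpatient treatment and ATLAS severity.

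**The opposite-effects illustration is extreme and depends on the split.** This also stands. A reader might infer that CMH usually misses opposite effects. That holds only for near-equal subgroups, where the effects cancel. At 80/20 CMH rejects in about half of trials and at 90/10 in about three quarters, because the larger subgroup dominates. The argument that does not depend on the split is the 91% rejection rate when the effects are identical.

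**Subgroups feed no decision rule.** Correct. Success rests on posterior-probability thresholds, and closed testing covers only the primary and secondary endpoints.

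**Conclusion.** The point holds: the test named in 8.8 does not test what 8.8 says it tests. At the plan's rates and 160/80 subjects, CMH rejects in about 91% of trials under perfect homogeneity, where a proper test rejects in about 5%. This follows from the null hypothesis of CMH and does not depend on subgroup sizes. The figures for opposite effects do depend on them, and the vancomycin-duration ranges rest on assumed shares.

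The practical gap is narrow. For the main list, 7.6.1.2 supplies a valid interaction analysis where its size condition is met. For the vancomycin-duration split, and for optional subgroups outside that model, the CMH sentence is the only stated heterogeneity test. A reader might take this as a threat to the trial's efficacy conclusion. The documents do not support that: type I error, sample size and the primary and secondary decisions are untouched, and the subgroup estimates would still be reported. It should be corrected, as a matter of supportive analysis.

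**What to change.** Replace the last sentence of SAP 8.8 with: *Homogeneity of the odds ratios across subgroups will be assessed with the Breslow-Day test (Tarone-adjusted), or a treatment-by-subgroup interaction test from a logistic model, including for the vancomycin-duration subgroup and any optional subgroup analysed.* Keep CMH only for a stratum-adjusted common odds ratio, if one is wanted.

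The cost is one sentence, with no effect on data collection, sample size, or the primary and secondary analyses. Make the change before unblinding, so that the choice of test cannot appear data-driven.

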9 COMPUTER SOFTWARE

All analyses will be performed by Medpace using Version 9.3 or later of SAS® software. All summary tables and data listings will be prepared utilizing SAS® software.

10 APPENDIX: BAYESIAN ANALYSIS PLAN

Adaptive Design Report for the Phase 3 Trial (2017-01) for Evaluating the Efficacy and Safety of Rebiotix RBX2660 (microbiota suspension) for the Treatment of Recurrent Clostridium difficile Infection

Submitted to Rebiotix

August 7, 2019

Introduction

This document describes the adaptive design for a randomized clinical trial to support administration of Rebiotix RBX2660 (microbiota suspension) via enema for the prevention of recurrent *Clostridium difficile* infection (CDI). The trial will enroll and treat up to 270 subjects with recurrent CDI and includes up to two interim analyses at a minimum of 160 and 220 subjects complete (i.e., completed the 8-week follow-up assessment and/or completion of Treatment Outcome form after receiving the blinded treatment). The first interim analysis may occur after 160 subjects complete, pending FDA review of the proposed adaptive design. Early trial success or failure may be declared at either of the interims depending on the strength (either positive or negative) of the observed data. The primary analysis of the trial will be a Bayesian hierarchical model, which formally incorporates data from a previous randomized Phase 2b study (Protocol 2014-01) of RBX2660.

Treatment Arms

Subjects will be randomized to one of the following treatments:

- Treatment: A single dosing of RBX2660 via enema
- Control: A single dosing of placebo via enema

A 2:1 randomization ratio will be used to incentivize patient enrollment in the trial.

Primary Analysis Population

The primary analysis will be conducted using the Modified Intent-to-Treat (mITT) population described in the statistical analysis plan (SAP). Subjects in the mITT population who withdraw due to CDI related symptoms will be counted as treatment failures. Up to 270 patients will be treated in the trial. Patients in the mITT population who dropout prior to completion will be treated as failures; the effect of dropout is described in the section **Operating Characteristics Under Dropout**.

Primary Endpoint

The primary endpoint of the trial is recurrence of CDI within 8 weeks of blinded treatment. Treatment success is defined as the absence of CDI diarrhea through 8 weeks after completing the blinded study treatment.

Statistical Model

Historical Data

The primary statistical analysis will use a hierarchical model to dynamically borrow information about the treatment effect from the previous Phase 2b trial (Protocol 2014-01). The efficacy objectives of the previous study were to assess the effectiveness of two dosing strategies of RBX2660 in patients with CDI. In one dosing group, patients received two enemas of RBX2660 (administered 7 ± 2 days apart). In the alternate dosing group, patients received a single enema of RBX2660 along with a placebo (administered 7 ± 2 days apart). Both treatments were compared to patients in a control arm who received 2 administrations of placebo via enema (administered 7 ± 2 days apart). Data from this trial are shown in Table 1.

Table 1: Data from Phase 2b trial (Protocol 2014-01).

Group	Dosing	# Subjects	# Responders	Response Rate
A	2 doses of RBX2660	41	25	0.610
B	Placebo	44	19	0.432
C	1 dose of RBX2660	42	25	0.595

The hierarchical model will incorporate data from groups B and C, excluding group A due to the difference in treatment dosage.

The patients enrolled in this study are expected to be enrolled from a population similar to the Phase 2b trial. In the case that subjects from the Phase 2b trial differ substantially from the current study, the proposed borrowing strategy allows for heterogeneity between study populations and dynamically borrows less information when the data from the new study differs from the Phase 2b study.

For example, one difference between the studies is that patients with a single recurrence of CDI may be enrolled in this trial whereas they were excluded from the Phase 2b trial. We expect that this change will minimally impact the baseline rate of CDI recurrence observed in the new study. However, if we did observe a control response rate that differed substantially from the Phase 2b study, the design would borrow less information, reducing the role of the historical data in our inference. This effect is described in the section **Strength of the Borrowing**.

Hierarchical Model

The data from the Phase 3 trial and Phase 2b trial will be analyzed using a Bayesian hierarchical model. The analysis will be conducted using a modified intent to treat population. Let $N_{k,s}$ be the number of subjects assigned to treatment k ($k = T$ for patients who receive a single dose of RBX2660 and $k = C$ for patients who receive the control) in study s ($s = 1$ for the current Phase 3 study, $s = 2$ for the previous Phase 2 study). We model the number of responders, $X_{k,s}$, in each arm/study as

$$X_{k,s} \sim \text{Binomial}(N_{k,s}, p_{k,s})$$

where $p_{k,s}$ is the underlying event rate for arm k in study s . The event rates are transformed to the log-odds scale and modeled as:

$$\log\left(\frac{p_{C,s}}{1 - p_{C,s}}\right) = \alpha_s$$

for the control arms and

$$\log\left(\frac{p_{T,s}}{1 - p_{T,s}}\right) = \alpha_s + \theta_s$$

for the treatment arms. The parameter θ_s represents the effect of RBX2660, relative to placebo, on the log-odds scale for trial s . Hierarchical models are used to borrow information about the treatment and control effects across studies. The following prior is used for the control rates across the two trials:

$$\begin{aligned} \alpha_s &\sim N(\alpha, \tau_\alpha^2) \quad \text{for } s = 1, 2 \\ \alpha &\sim N(0, 10^2) \\ \tau_\alpha^2 &\sim \text{Inverse Gamma}(0.001, 0.1) \end{aligned}$$

A similar prior is used for the treatment effects across the two trials:

$$\begin{aligned} \theta_s &\sim N(\theta, \tau_\theta^2) \quad \text{for } s = 1, 2 \\ \theta &\sim N(0, 10^2) \\ \tau_\theta^2 &\sim \text{Inverse Gamma}(0.01, 0.01) \end{aligned}$$

The priors on α and θ are chosen to be conservative and emphasize a prior assumption of a control response rate near 0.5 with a treatment effect centered around 0. The priors on the hierarchical variance terms τ_α^2 and τ_θ^2 are parameterized by their location μ and weight ω (rather than the traditional $shape = \omega/2$ and $scale = \mu^2 \cdot \omega/2$ parameterization). These priors were chosen to encourage dynamic borrowing between the studies. This distribution is defined by the density:

$$f(x|\mu, \omega) \propto \frac{e^{-\mu^2 \omega/2x}}{x^{\omega/2+1}}$$

The selection of the borrowing hyper parameters is discussed in the **Strength of the Borrowing** Section of this design report.

Success Criteria

Our primary interest lies in the treatment effect (TE) for the current Phase 3 study ($s = 1$):

$$TE = p_{T,1} - p_{C,1}$$

The primary goal of the trial is to demonstrate the efficacy of RBX2660 by testing the hypothesis:

$$H_0: TE \leq 0 \quad \text{vs.} \quad H_A: TE > 0$$

We test this hypothesis by calculating the posterior probability of superiority, $\Pr(TE > 0 | \text{Data})$, which is equivalent to $\Pr(\theta_1 > 0 | \text{Data})$. The thresholds for defining success at each analysis are summarized in Table 2.

Table 2: Success criteria at each analysis. The * indicates that the success criteria may be updated at the final analysis to ensure the correct amount of α –spend.

Analysis	Criteria	Subjects complete
Interim 1	$\Pr(TE > 0 \text{Data}) > 0.99943$	Minimum 160
Interim 2	$\Pr(TE > 0 \text{Data}) > 0.99943$	220
Final	$\Pr(TE > 0 \text{Data}) > 0.99943^*$	Maximum 270
Final	$\Pr(TE > 0 \text{Data}) > 0.97706$	Maximum 270

The success criteria of 0.99943 was chosen using a Pocock spending function for analysis performed at 160, 220, and 270 patients complete with a cumulative α spend of 0.00125. Success at this level is considered appropriate for approval based on results from a single trial.

Uncertainty from several factors make assessing the exact α –spend at each analysis difficult to quantify. First, the definition of the mITT population allows for the final analysis to be performed with fewer than 270 complete subjects. In addition, the first interim analysis may be performed when more than 160 subjects are enrolled and treated. Finally, the second interim analysis may be omitted if the first interim analysis occurs sufficiently close to 220 subjects enrolled. Therefore, to account for this uncertainty, the success criteria at the final analysis will be updated to reflect the information spend at each interim analysis and ensure a cumulative α spend of 0.00125. This change will be made based on the fraction of information at each interim analysis and does not depend on the outcome data for the trial.

The lower, secondary, threshold of 0.97706 at the final analysis allows for success at the less demanding $\alpha = 0.025$ level. The second threshold at the final analysis controls the overall Type I error rate for the trial at 2.5% (without borrowing), accounting for the α spend at the interims and higher look at the final analysis.

Futility Stopping

The trial will stop for futility at either interim if the predictive probability (PP) of success at the final analysis is sufficiently small. The predictive probabilities will be computed using a final threshold of 0.97706 and assuming a final enrollment of 270 subjects. Bayesian predictive distributions incorporate the uncertainty around the model parameters as well as the uncertainty in the outcomes of subjects not yet enrolled. The trial will stop for futility if there is limited probability that the trial will reach the success criterion, even at the maximum sample size. The criteria for declaring futility at each interim are shown in Table 3.

Table 3: Futility criteria at each analysis.

Analysis	Criteria	Subjects complete
Interim 1	PP(Success) < 0.01	Minimum 160
Interim 2	PP(Success) < 0.01	220

Strength of the Borrowing

The hyper-priors on τ_α^2 and τ_θ^2 are chosen to encourage dynamic borrowing from the Phase 2b trial. Dynamic borrowing is the idea that when the observed data in the current trial is similar to the previous trial, the strength of our conclusions should increase. On the other hand, if the newly observed data is quite different from the previous data, the prior data should contribute less information to our inference.

Consider two extremes. The first is the case of full borrowing, where data from the previous study is added to data from the new trial and inference is performed using the full weight of both studies. Alternatively, we could do no borrowing, ignoring information from the previous trial and conducting our analysis with only the new information. The hyper-priors on τ_α^2 and τ_θ^2 are specified to provide dynamic borrowing, behaving similarly to the full borrowing approach when the observed data resembles the Phase 2b data and mimicking the no borrowing approach when the results differ in the two trials. The effect of the dynamic borrowing is illustrated in Figure 1.

Figure 1: Effective sample size (ESS) borrowed on the treatment arm for different observed treatment and response rates at the first interim.

[figure not shown]

Figure 1 summarizes the amount of borrowing from the hierarchical model for different observed treatment success proportions ($X_{T,1}/N_{T,1}$, the x-axis) and different observed control proportions ($X_{C,1}/N_{C,1}$, differently colored lines). At the first interim analysis, 104 subjects are assumed to be enrolled to the treatment arm with 56 subjects enrolled in the control arm. The y-axis shows the effective number of additional treatment patients borrowed by the model, given by the equation

$$\text{Additional patients} = \frac{\text{Var}(\theta_{full})}{\text{Var}(\theta_1)} (N_1 + N_2) - N_2$$

The quantity $\text{Var}(\theta_1)$ is the posterior variance of the treatment effect under the hierarchical model and $\text{Var}(\theta_{full})$ is the variance of the treatment effect under the full borrowing model. The ratio of these terms is the relative effective sample size, which measures the uncertainty in the hierarchical model relative to the full model. When this ratio is small, there is substantially more uncertainty in the hierarchical model compared to the full model.

The horizontal dashed lines correspond to 0 (no borrowing from the Phase 2b data) and 86 (full borrowing of the Phase 2b data of Groups B and C). The hierarchical model borrows the most patients from the Phase 2b trial when the observed treatment response rate is close to the treatment response rate in the previous study (a rate of 0.595). As the observed control rate differs from the historical rate, fewer additional patients from the previous trial are used and the amount of borrowing diminishes. When the observed control rate differs from the historical rate, borrowing is strongest when the log-odds of the treatment effect are similar to the phase 2b data. The chosen hyper-priors create appropriate dynamic behavior, decreasing uncertainty when then observed data is in concordance with the previous trial and increasing uncertainty when the Phase 3 trial results differ from the Phase 2b trial.

Example Trials

[figure not shown]
This section contains several example trials selected to highlight aspects of the analysis and design. For each example trial result, we show the following information at each analysis.

- **Observed data:** a bar plot showing the number of patients with complete data enrolled per arm (total width of the bar) as well as the number of responders (darker shaded region).
- **Credible intervals:** plot showing the fitted response rate for each arm (the X) and 95% credible interval for each arm.
- **Pr(Treatment > Control):** the posterior probability of a positive treatment effect in the Phase 3 trial, used for declaring trial success according to Table 2.
- **Pr(Success at N = 270):** the predictive probability of success at the final analysis. The trial stops for futility when this probability drops below 0.001.
- **Pr(Treatment Response):** posterior mean of the treatment arm response probability
- **Pr(Control Response):** posterior mean of the control arm response probability

Example Trial 1

The first interim occurs when the minimum of N=160 subjects have complete data (i.e., completed their 8-week follow-up assessment and/or completion of Treatment Outcome form after receiving the blinded treatment). Example 1.1 shows the status of the trial at the first interim.

Example 1.1: Status of the trial at the 1st interim

[figure not shown]

The response rate on the control arm is 44.4%, which is similar to the Phase 2b data, and the response rate on the treatment arm is 69.8%, which is larger than observed in the Phase 2 trial. The posterior estimates of the treatment response rate are smaller than the observed rate due to the borrowing from the Phase 2b data. The posterior probability of a positive treatment effect exceeds 0.99943 and success is declared.

Example Trial 2

[figure not shown]
The first interim occurs when N=170 subjects have complete data. Example 2.1 shows the status of the trial at the first interim.

Example 2.1: Status of the trial at the 1st interim

The observed response rates in this scenario are much smaller than in the Phase 2b data, with an observed treatment effect of 0.066. While the predictive probability of success is small (0.324), it is sufficient to continue the trial to the second interim.

Example 2.2: Status of the trial at the 2nd interim

[figure not shown]

The second interim, shown in Example 2.2, occurs when 220 patients have complete data. The observed response rates have increased in both arms, though the observed treatment effect is smaller (0.014). While the estimated treatment effect is positive, the probability of declaring success at the final analysis is 0.003 which is sufficiently small to stop the trial for futility.

Example Trial 3

In this example, the first interim analysis occurs when 180 subjects have been enrolled. The observed control rate is 0.5, somewhat higher than seen in the Phase 2b trial. Example 3.1 shows the status of the trial at the first interim

[figure not shown]
Example 3.1: Status of the trial at the 1st interim

The posterior estimate of the control response rate (0.473) is somewhat lower than

[figure not shown]
observed due to the borrowing and the posterior probability of a treatment effect is insufficiently high to declare success at the first interim.

Example 3.2: Status of the trial at the 2nd interim

At the second interim (N=220, shown in Example 3.2), the observed response rates in both arms have been reduced. The trial has not shown sufficient evidence to declare success or futility and continues enrollment, though the predictive probability of success at the final analysis remains optimistic (0.797).

Example 3.3: Status of the trial at the final analysis

The final analysis is conducted when 270 patients have completed follow-up and 260 subjects qualify for the mITT population (Example 3.3). The single trial success criteria is updated to 0.99931, using the information fraction and 0.99943 criteria at the first two interims (0.692 and 0.846) to ensure an overall α –spend of 0.00125. The trial is declared a success at the 0.025 level, though it does not meet the single trial success criteria.

Performance Characteristics

The performance characteristics of the design were determined through trial simulation. We assume several scenarios for the underlying response probability for the control and treatment arms, considering control probabilities in $\{0.2, 0.3, 0.4, 0.45, 0.5, 0.6, 0.7\}$ and additive treatment effects of $\{0.0, 0.05, 0.1, 0.15, 0.2, 0.25, 0.3\}$. The scenario with a control probability of 0.45 and a treatment effect of 0.15 corresponds most closely to what was observed during the Phase 2b trial. The scenarios with treatment effects of 0 correspond to null scenarios. For the purposes of simulation, we assume that patients are randomized in 3 patient blocks, that interim analysis were performed with exactly 160 and 220 subjects completed, and that the 270 mITT subjects have complete data at the final analysis.

Operating Characteristics

We simulated 1,000,000 virtual trials for each scenario. The results of the simulations are summarized using the following operating characteristics.

- **Pr(Success):** the cumulative probability of declaring success at the analysis. For example, Pr(Success) under the section Interim 2 includes the probability of declaring success at either Interim 1 or Interim 2. For the final analysis, Pr(Success) (0.99943) and Pr(Success) (0.97706) include the cumulative probability of declaring success at the single trial and lower success levels respectively.
- **Pr(Futility):** the cumulative probability of declaring futility at the analysis
- **# Subjects:** the average number of subjects enrolled in the trial
- **Bias:** the average error in estimating the true (simulated) treatment effect.

Table 4 shows an example set of operating characteristics when the simulated control response probability is 0.45.

Table 4: Operating characteristics of the design when the underlying control response probability is 0.45.

Effect	Interim 1		Interim 2		Final analysis	
	Pr(Success)	Pr(Futility)	Pr(Success)	Pr(Futility)	Pr(Success) (0.99943)	Pr(Success) (0.97706)
0	0.001	0.445	0.001	0.732	0.002	0.042
0.05	0.006	0.204	0.012	0.424	0.018	0.204
0.1	0.037	0.065	0.072	0.158	0.106	0.528
0.15	0.141	0.014	0.257	0.036	0.354	0.833
0.2	0.363	0.002	0.564	0.005	0.695	0.969
0.25	0.651	0.000	0.838	0.000	0.919	0.997
0.3	0.868	0.000	0.965	0.000	0.989	1.000

Under the null scenario where both the control and treatment arms have a 45% true response rate, 45% of trials stop for futility at the first interim analysis ($N = 160$) and 0.1% of trials meet the success criterion. By the second interim, 73% of trials have stopped for futility. Assuming a final threshold of 0.97706, the probability of trial success at or before the final analysis is 0.042. The type I error of this trial is inflated beyond the nominal 2.5% level because of the borrowing from the positive phase 2 data.

In the scenario with a treatment effect of 0.15 (which most closely reflects the observed data from Phase 2), the trial has 83% power. Broken down by analysis, 14% of trials declare success at the first interim, another 12% of trials declare success at the second interim, 9% of trials reach the higher success threshold of 0.99875 at the final analysis and 48% of trials declare success at the lower hurdle at the final analysis. When the true

[figure not shown]
effect is 0.10, the overall power drops to 52% with 77% of trials progressing to the final analysis.

